2.3 Exploratory Objective(s) & Hypotheses

Objectives

- (1) To describe the demographic and clinical characteristics among all patients who received germline testing and subsequently, stratify by presence of germline mutations in cancer susceptibility genes.

Hypotheses

- (1) We hypothesize that patients with pathogenic germline alteration have more aggressive disease patterns in both the localized and advanced settings.

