3.3 Inclusion Criteria

1. Men, age greater than or equal to 18 years of age.
2. Diagnosis of prostate cancer of any histology.
3. Must meet NCCN guidelines for germline testing (see table below for specific definition of risk groups).
 - a. Men with very low, low or intermediate risk prostate per NCCN guidelines with a positive family history or intraductal histology OR

- Family history here is considered significant if the patient has a first degree relative with prostate cancer or more than one first/second degree relative with prostate cancer.
- ≥3 cancers on same side of family, especially diagnoses ≤50 years of age: bile duct, breast, colorectal, endometrial, gastric, kidney, melanoma, ovarian, pancreatic, prostate (but not clinically localized Grade Group 1), small bowel, or urothelial cancer
- b. Men with high-risk, very-high risk (see Table 3 for NCCN definitions of risk groups), lymph node positive, or metastatic prostate cancer independent of family history of histology.

NCCN definitions of risk groups in localized prostate cancer

Risk group	Clinical/pathologic features			Imaging ^{h,i}	Germline testing
Very low ^f	
 • T1c AND • Grade Group 1 AND • PSA <10 ng/mL AND • Fewer than 3 prostate biopsy fragments/cores positive, ≤50% cancer in each fragment/core^g AND • PSA density <0.15 ng/mL/g 			Not indicated	Recommended if family history positive or intraductal histology See PROS-1
Low ^f	
 • T1-T2a AND • Grade Group 1 AND • PSA <10 ng/mL 			Not indicated	Recommended if family history positive or intraductal histology See PROS-1
Intermediate ^f	Has no high- or very-high-risk features and has one or more intermediate risk factors (IRF):	Favorable intermediate	
 • 1 IRF and • Grade Group 1 or 2 and • <50% biopsy cores positive^g 	
 • Bone imaging^j: not recommended for staging • Pelvic ± abdominal imaging: recommended if nomogram predicts >10% probability of pelvic lymph node involvement • If regional or distant metastases are found, see PROS-9 	Recommended if family history positive or intraductal histology See PROS-1

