4.2 Outcomes

Primary Endpoints

1. The proportion of patients who undergo germline testing among those who are enrolled to the study compared to the proportion of patients who undergo germline testing who were eligible, but not enrolled into this study during the study time period
2. Feasibility of implementing an educational intervention for men with prostate cancer at risk of having a hereditary cancer syndrome. This will be assessed by:
 - Accrual rate by month.
 - Proportion of patients who consent to educational intervention among those who are approached (stratified by whether consent was performed in-person or virtually).

Secondary Endpoints

1. Patient understanding of germline testing before and after the education intervention based on questionnaire responses.
2. Patient-reported opinions on germline testing before and after intervention, and patient-reported satisfaction after educational intervention based on questionnaire responses.
3. Physician responses regarding how the germline testing result changed patient management.
4. Prevalence of pathogenic germline mutations among study patients who undergo germline testing.

Exploratory Endpoints

1. Clinical factors (patient and family history, disease characteristics, and outcomes) that are associated with the presence of a germline mutation in a cancer susceptibility gene.

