4.4 Statistical Analysis Plan

4.5 Statistical Methods – General Aspects

4.5.1 Primary Objective(s): Calculation of Epidemiological Measure(s) of Interest (e.g. descriptive statistics, hazard ratios, incidence rates, test/retest reliability)

Primary Endpoints

With regards to the primary endpoint, at the completion of the study, the proportion of patients who complete germline testing among all who are enrolled to the study will be computed. A sample size of 50 patients produces a two-sided 95% confidence interval on the proportion with a width ranging from 0.27 to 0.29 when the observed proportion ranging from 0.3 to 0.7. For proportions, 95% confidence intervals will be calculated using the exact method.

We will also compute the proportion of patients who completed germline testing for all eligible prostate cancer patients evaluated in clinic but not enrolled into this study during the study period. Characteristics between these two groups will be compared using Fisher's Exacts or Wilcoxon Rank Sum tests. The proportion of patients who underwent germline testing in the intervention vs non-intervention cohorts will be compared using Fisher's exact test.

4.5.2 Secondary Objective(s): Calculation of Epidemiological Measure(s) of Interest (e.g. hazard ratios, incidence rates, test/retest reliability)

Secondary endpoints including germline mutation frequency, patient understanding of germline testing, and medical management from germline testing will be described using descriptive statistics such as bar graphs, box plots, percentages, means and standard deviations, etc.

4.5.3 Exploratory Objective(s): Calculation of Epidemiological Measure(s) of Interest (e.g. hazard ratios, incidence rates, test/retest reliability)

- Associations between clinical factors and pathogenic germline alterations will be evaluated using Odds Ratio.
- Impact of germline testing on prostate cancer and cancer surveillance management will be qualitatively described.

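### Odds ratios for carrier status pooled over both entry routes are distorted by the eligibility rule: the family-history odds ratio is pulled down, and the localized aggressiveness contrast is attenuated if the entry features are linked to carriage

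*Combined protocol and SAP*

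**What the plan says.** Inclusion criterion 3 (Section 3.3) has two routes. Route 3a admits "Men with very low, low or intermediate risk prostate per NCCN guidelines with a positive family history or intraductal histology". Route 3b admits high-risk and very-high-risk men and those with "lymph node positive, or metastatic prostate cancer independent of family history of histology". For 3a, "Family history here is considered significant if the patient has a first degree relative with prostate cancer"; alternatives are more than one affected first- or second-degree relative, or at least three listed cancers on one side of the family.

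The exploratory endpoint (Section 4.2) is "Clinical factors (patient and family history, disease characteristics, and outcomes) that are associated with the presence of a germline mutation". The hypothesis in Section 2.3 is that "patients with pathogenic germline alteration have more aggressive disease patterns in both the localized and advanced settings", and the objective there covers every man who was tested. The whole analysis instruction, in Section 4.5.3, is that "Associations between clinical factors and pathogenic germline alterations will be evaluated using Odds Ratio". No stratification by entry route, restriction, adjustment or target population is given. Sections 4.6.1 and 4.6.3 discuss bias from clinic screening, language and visit format, but not from the eligibility rule.

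**The concern.** Two factors to be related to carrier status, family history and risk group, also decide who enters. Lower-risk men are all selected on family history or intraductal histology; 3b men are not. This has two consequences if all tested men go into one table.

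- **Family history.** The group without it is almost entirely 3b, with the higher carrier rates. The group with it also contains the 3a men, whose risk group has the lowest rate in Table 1. The comparison mixes family history with stage, and the odds ratio is pulled down.
- **Aggressiveness, localized setting.** The low/intermediate reference group consists only of men with a feature that may raise carrier probability. If it does, the high versus low/intermediate odds ratio shrinks.

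More patients would not remove either effect. At stake is a reported finding of no association, or of apparently protective family history, that the entry rule produced.

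**Working it through.** **The plan's own figures.** The only design calculation (Section 4.8) is the 95% interval width at n = 50. The exact method gives 0.2675 at proportions 0.3 and 0.7, and 0.2895 at 0.5, which matches the stated 0.27 to 0.29. It does not concern the odds ratios.

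**Inputs from Table 1.** Low-intermediate risk 4/162 (2.5%, odds 4/158); high risk 19/337 (5.6%, odds 19/318); metastatic 11.8% as printed (84/692 is 12.1%, but 84 counts mutations).

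**Assumed, not in the documents.** Case mix; family-history prevalence; strength of the link between family history and carriage.

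**1. Family-history odds ratio**

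Take 25 metastatic, 15 high-risk and 10 lower-risk men, all of the last entering through family history. Let family history be present in 20% of non-carriers and 40% of carriers. True odds ratio = (0.4/0.6)/(0.2/0.8) = 2.67.

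- 3b carriers: 25 × 0.118 + 15 × 19/337 = 3.80; non-carriers: 40 − 3.80 = 36.20.
- 3a carrier odds: (4/158) × (0.4/0.2) = 0.0506, so probability 0.0482; 0.48 carriers and 9.52 non-carriers, all with family history.

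| | Carriers | Non-carriers |
|---|---|---|
| Family history | 0.4 × 3.80 + 0.48 = 2.00 | 0.2 × 36.20 + 9.52 = 16.76 |
| None | 0.6 × 3.80 = 2.28 | 0.8 × 36.20 = 28.96 |

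Pooled odds ratio = (2.00/16.76)/(2.28/28.96) = 1.52. Within 3b alone it is (1.52/7.24)/(2.28/28.96) = 2.67, the true value.

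The same steps for other cases give:

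| Metastatic / high-risk / lower-risk | True 2.67 becomes | True 1.0 becomes |
|---|---|---|
| 25 / 15 / 10 | 1.52 | 0.56 |
| 30 / 15 / 5 | 1.91 | 0.71 |

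**2. Localized aggressiveness odds ratio**

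Source value from Table 1: (19/318)/(4/158) = 2.36.

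Let f be family-history prevalence and R the family-history/carrier odds ratio, with family history independent of risk group and acting equally in both. In low/intermediate men, solve for the carrier odds o without family history:

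f × Ro/(1 + Ro) + (1 − f) × o/(1 + o) = 4/162.

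After selection the reference group has odds Ro. At f = 0.2 and R = 2, o = 0.0212 and Ro = 0.0423, so the observed odds ratio is 0.0597/0.0423 = 1.41. Across f from 10% to 30%:

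| R | Odds ratio under the entry rule |
|---|---|
| 1 | 2.36 (no bias) |
| 1.5 | 1.65-1.81 |
| 2 | 1.30-1.53 |
| 3 | 0.94-1.25 |
| 4 | 0.76-1.11 |

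Adding the intraductal route (assumed 3% of lower-risk and 10% of high-risk men, carrier odds ratio 2) gives 1.42 at f = 0.2 and R = 2, and 2.15 at R = 1.

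**3. Sampling error**

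- If all 50 men are tested, 50 × 6% = 3 to 50 × 11.8% = 5.9 carriers are expected.
- For the pooled 1.52, the standard error of the log odds ratio is √(1/2.00 + 1/16.76 + 1/2.28 + 1/28.96) = 1.02, giving 95% limits of about 0.2 to 11.
- For the 3b-only 2.67 it is √(1/1.52 + 1/7.24 + 1/2.28 + 1/28.96) = 1.13, giving limits of about 0.3 to 24.

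**4. A contrast among men who all meet the 3a condition**

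Comparing low/intermediate with high-risk men who all have family history also removes the bias in principle. In the scenario of step 1 it would compare 10 men with about 3 (0.4 × 0.85 + 0.2 × 14.15 = 3.17), with 0.48 + 0.34 = 0.82 expected carriers. The chance that both groups contain a carrier is about 0.39 × 0.30 = 0.12. It cannot be estimated.

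**The case against.** **Pooling is read from silence.** Section 4.5.3 does not say how the odds ratios are grouped, and the hypothesis names localized and advanced settings separately. That is fair. But the objective takes in all tested men, and splitting by setting would still leave 3a and 3b men together in the localized group.

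**Crude odds ratios are valid for guideline-eligible men.** This stands as a description. The hypothesis is worded for carriers in general, however, and no such limit is stated.

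**Both odds ratios are biased whatever the truth.** A reader might infer this, but it does not hold for aggressiveness: if neither entry feature relates to carriage, 2.36 stays 2.36. The documents give no family-history/carrier odds ratio. The Table 2 remark on low yield concerns absence of family history or of clinical features, and lists high risk among those features, so it does not isolate family history.

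**The entry rule reverses the aggressiveness association.** A reader might infer this too. Dividing 2.36 by the ratio of family-history prevalence in carriers to that in non-carriers gives 0.79 at a ratio of 3 and 0.59 at 4. At 20% prevalence in non-carriers, those ratios mean 60% and 80% in carriers, or odds ratios of 6 and 16. Attenuation is the defensible statement; a value at or below 1 needs a strong link.

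**It is immaterial at this size.** Largely conceded. A shift from 2.67 to 1.52 is invisible within limits of 0.2 to 11, and the 2.36 itself rests on four low/intermediate carriers (95% limits about 0.8 to 7.1). This lowers the priority but does not make the pooled contrast interpretable.

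**Conclusion.** The point holds as a minor, exploratory-level one. Pooled over entry routes, the family-history odds ratio is pulled down given Table 1's carrier gradient, even when family history is unrelated to carriage. Its size depends on the assumed case mix: 2.67 becomes about 1.5 to 1.9, and 1.0 becomes about 0.56 to 0.71.

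The localized high versus low/intermediate odds ratio is attenuated only if family history or intraductal histology is associated with carriage: to roughly 1.3-1.5 at an assumed odds ratio of 2, and near 1 at 3. Contrasts wholly within 3b, including those in the advanced setting, are not affected by this rule.

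A reader might go further and conclude that the study's main results are compromised. They are not: the primary and secondary endpoints do not use these odds ratios, and sampling error with about 3-6 carriers exceeds the bias.

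**What to change.** In Section 4.5.3:

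1. Derive the qualifying route, 3a or 3b, for every tested man. Section 4.3 already collects family history, histology, grade, PSA, stage and metastatic sites.
2. Estimate the family-history odds ratio within 3b men only, and likewise aggressiveness odds ratios such as metastatic versus high-risk localized.
3. Describe 3a men separately, without an odds ratio among men meeting the 3a condition; too few carriers are expected.
4. State that any pooled low/intermediate versus high-risk odds ratio applies only to NCCN-eligible men, is affected by the entry rule, and is not a test of the localized-setting hypothesis.

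The cost is a few sentences and one derived variable. The downside is slightly fewer men in each odds ratio (40 rather than 50 in the worked scenario) and somewhat wider intervals. No new data collection is needed.

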4.6 Bias

4.6.1 Methods to Minimize Bias

We aim to reduce bias through several methods including systematically screening medical oncology and urology clinics to identify eligible patients. The research coordinator will have a rotating schedule of clinics to screen to ensure systematic non-bias selection of eligible patients. Additionally, the intervention will be offered in multiple media modalities including in-person, video, and telephone to accommodate patient preferences. The intervention and video will be available in English and Spanish to further limit selection bias. Furthermore, there is capacity to perform the intervention in the clinic coinciding with the patients clinic appointment or at a separate time that is feasible for the patient.

4.6.2 Adjustment for Multiple Comparisons

Not applicable.

4.6.3 Strengths and Limitations

The primary strength of the study is the novel approach to integration of germline testing education into the clinic. The study will assess the feasibility of an in clinic educational model led by a clinical research coordinator. This will also assess the feasibility of how other clinicians outside of genetics can provide some degree of genetic counselling that could be applicable to medical assistants, nurses, and advanced practice providers.

A key limitation of this study include bias with regards to recruitment, which we hope to mitigate by offering the study to all eligible patients in all GU oncology clinics, offering the session in English and Spanish, and offering a virtual option.

4.7 Interim Analyses (Optional)

N/A

4.8 Sample Size and Power Calculations

With regards to the primary endpoint, at the completion of the study, the proportion of patients who complete germline testing among all who are enrolled to the study will be computed. A sample size of 50 patients produces a two-sided 95% confidence interval on the proportion with a width ranging from 0.27 to 0.29 when the observed proportion ranging from 0.3 to 0.7.

5. STUDY CONDUCT AND REGULATORY DETAILS

5.1 Study Conduct

5.1.1 Study Flow Chart and Plan

Scheduled of Assessments			
	Pre- Study	Intervention	Follow Up
Family History Questionnaire		X	
Pre-Intervention Patient Questionnaire		X	
Educational Session		X	
Post Intervention Patient Questionnaire		X	
Germline Results Review			X
Clinician Questionnaire			X

5.1.2 Procedures

Recruitment:

Pre-screening procedures will involve the review of subject records by designated study personnel in order to identify potentially eligible subjects. Protected health information (PHI): Patient Name, Medical Record Number, Date of Birth, date and time of upcoming appointments, medications, and disease status, will be accessed via the hospital's medical record database and scheduling system prior to contacting the potential subject about the research study. The Slicer Dicer Epic functionality may also be utilized to identify eligible patients in addition to systematic review of clinician schedules. A partial waiver of HIPAA authorization for access to PHI for purposes of pre-screening is being requested. This study meets the following requirements for this request per 45 CFR 164.512(i)(2)(ii):

1. The use or disclosure of PHI involves no more than minimal risk to the privacy of individuals as the only risk is loss of confidentiality and all reasonable measures to protect confidentiality will be carried out.

2. Granting of the waiver will not adversely affect privacy rights and welfare of the individuals whose records will be used as the only risk is loss of confidentiality and all reasonable measures to protect confidentiality will be carried out.
3. The pre-screening could not practicably be conducted without a waiver because we need to search project the EPIC electronic database to identify eligible subjects.
4. The project could not practicably be conducted without use of PHI because demographic and clinic information are needed in order to identify eligible subjects.
5. The privacy risks are low relative to the anticipated benefits of research. The privacy risks are minimal since all reasonable efforts to protect confidentiality will be performed and there is the potential to gain scientific knowledge that will benefit future genitourinary cancer patients.
6. An adequate plan to protect identifiers from improper use and disclosure is included in this research proposal.
7. An adequate plan to destroy the identifiers at the earliest opportunity is included in the research proposal.
8. The PHI will not be re-used or disclosed for other purposes.

A partial waiver of informed consent is being requested for pre-screening. The reasons underlying this request include the following per 45 CFR 46.116:

1. The (pre-screening) research involves no more than minimal risk to the subjects as the only risk is loss of confidentiality and all reasonable measures to protect confidentiality will be carried out;
2. The waiver will not adversely affect the rights and welfare of the subjects used as the only risk is loss of confidentiality and all reasonable measures to protect confidentiality will be carried out;
3. The (pre-screening) research could not practicably be carried out without the as the research staff needs to search the EPIC electronic database to identify eligible subjects; and
4. Whenever appropriate, the subjects will be provided with additional pertinent information after participation.

Informed Consent:

Individuals who fulfill the eligibility criteria will be offered participation in this study. The patient's treating physician will authorize the investigator or study coordinator to meet with the patient. Consent may occur in-person, via video chat, or via telephone. Study candidates will be asked to provide written consent, using an IRB-approved informed consent form. The investigator or study coordinator will describe the study to potential participants. The investigator or study coordinator will provide potential participants with a blank informed consent form. The individual will be given ample time to read this consent form at the same visit or may take it with them to read at another time. The study candidate will be given the opportunity to ask and receive answers to all questions they may have about the study, its risks and benefits, and the consent form itself before signing the consent form. As this research is subject to HIPAA Privacy Rule provisions, study candidates will also be requested to sign a separate HIPAA authorization form specific to the research study for the use of PHI. The consent process will be appropriately documented.

Survey Administration:

All surveys will be available as secure links sent to the participant's provided email through REDCap. The patients can also opt to complete the surveys by phone with the research assistant or on paper.

Family History Questionnaire: The Family History Questionnaire (FHQ) is the standard method of self-reported data collection for patients at in the Genitourinary Program at UCSD. This has been modeled from Family History Questionnaires utilized within our Cancer Genetics Program at UCSD and others across the country but modeled for men with prostate cancer.

Pre-Intervention Patient Questionnaire: The pre-intervention patient questionnaire is a brief 16-item investigator-developed knowledge and attitude scale applicable to this population. It was developed through an expert panel to determine if participants are able to recall key core components about multi-gene panel testing and capture attitudes about genetic testing. This survey is estimated to take 10 minutes to complete.

Post-Intervention Patient Questionnaire: The post-intervention patient questionnaire is a brief 24-item investigator-developed knowledge and attitude scale applicable to this population. It includes the same 14 knowledge and attitude items from the pre-intervention survey to assess impact of the educational intervention. It was developed through an expert panel to determine if participants are able to recall key core components about multi-gene panel testing and capture attitudes about genetic testing. There is also a 10-item scale to capture satisfaction with educational intervention. This survey is estimated to take 10 minutes to complete.

Post-Results Clinician Questionnaire: The post-result clinician questionnaire is a brief 6-item investigator-developed scale to assess whether the genetic testing results altered clinical practice for any given patient including change in disease monitoring, change in recommended treatment, referral to genetic counseling and other parameters. This survey is estimated to take 5 minutes to complete.

Intervention Administration:

The educational intervention including video and brochure review will be administered by a study team member in a consult or exam room on a password-protected tablet or on a computer when performed in person. For remote visits, a study team member will provide the participant with either an electronic or paper copy of the brochure for review and will share the educational video electronically via video functionality of EPIC or Doximity with the patient. For patients who prefer a telephone intervention, the video will still be made audible but not visible to the patient for review. The participant may choose to proceed or decline genetic testing after the educational intervention. If the participant has any questions regarding the study, the study team member may answer them. If the participant has any concerns or questions about genetic testing, the study team member will refer them to the educational materials provided, their clinician, or connect them to the Principal Investigator.

Withdrawal of Participation:

A participant is free to withdraw from the study at any time for any reason without prejudice to his future medical care by the physician or at the institution. If the participant decides that he does not want to continue to be a part of this study, he will contact PI [name] or the study coordinator. Their previously data will be destroyed if requested by the participant. In some cases, it may be impossible to stop future if the resulting data have already been analyzed and/or shared.

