2.2 Secondary Objective(s) & Hypotheses

Objectives

- (1) To assess patients' baseline knowledge of germline testing and the change in knowledge of germline testing with the educational intervention.
- (2) To assess a patient's baseline attitudes towards germline testing and assess the impact of an education interventional on patient perceptions of germline testing.
- (3) To assess the impact of germline testing results on prostate cancer management.
- (4) To assess prevalence of pathogenic germline mutations in patient population.

Hypotheses

- (1) We hypothesize that the educational intervention will lead to an improvement in knowledge of germline testing.
- (2) We hypothesize that the educational intervention will lead to a more favorable attitude towards germline testing among patients enrolled in the study.
- (3) We hypothesize that the educational intervention will result in greater prescribing of targeted therapies given detection of germline alterations in the HRR pathway.
- (4) We hypothesize that the educational session will improve patient's perception and familiarity with germline testing.

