The patient will then have an opportunity to ask questions. If a patient wishes to proceed with testing, they will sign the standard consent to proceed with germline testing and the patient's clinician will be notified of intent to proceed with germline testing. Patients can elect to decline testing, defer testing to a later time, or request referral to genetic counseling to discuss the testing. We will track patterns of patient decision making following the educational intervention. Upon a patient deciding to pursue testing, testing will consist of a prostate cancer germline panel with a commercially available blood or saliva-based assay. Following the educational intervention, the patient will be asked to complete a short patient education and satisfaction questionnaire (Appendix D). Upon receipt of the results, the coordinator will alert the patient's clinician, who will then share the results with the patient either in clinic or by phone. If the results show a

pathogenic germline mutation, the patient will be referred to see the UCSD cancer medical genetics clinic for consultation with a genetics counselor. Additionally, the patient can elect to see a genetics counselor independent of the test results once the test results are reviewed. If a patient pursues genetic testing, following receipt of results, the patient's clinicians will be asked to complete a short survey on to assess how the results of germline testing affected the patient's current and future management (appendix D). There will be capacity for patients to complete questionnaires electronically. Additionally, to systematically understand the scope of questions asked by patients which will provide opportunity to optimize the educational intervention, we will record the educational sessions.

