Appendix D: Post Results Clinician Questionnaire

Clinician Name: _____ Date: _____

Patient/Patient Study ID: _____

1. Did you find the germline test result helpful in the management of this patient?

- A) Yes
- B) No
- C) Unsure

2. Did the results of germline testing change your management of this patient currently?

- A) Yes
- B) No
- C) Unsure

3. Will the results of the testing change your management of this patient in the future?

- A) Yes
- B) No
- C) Unsure

4. Did the results of this testing change your perception of the patient's prognosis?

- A) Yes
- B) No
- C) Unsure

5. Did the results of this testing lead to further diagnostic testing or referrals?

- A) Yes
- B) No
- C) Unsure

6. If you have any additional feedback about the results or educational intervention with regards to this patient's case, please feel free to share:

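### The clinician questionnaire has no separate item for the three kinds of management change that section 5.1.2 says it covers, so secondary endpoint 3 shows whether management changed but not how

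*Combined protocol and SAP*

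**What the plan says.** Secondary objective 3 (section 2.2) is "To assess the impact of germline testing results on prostate cancer management". The matching endpoint in section 4.2 is "Physician responses regarding how the germline testing result changed patient management". The related hypothesis in section 2.2 expects "greater prescribing of targeted therapies given detection of germline alterations in the HRR pathway".

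Section 5.1.2 describes the instrument: "The post-result clinician questionnaire is a brief 6-item investigator-developed scale". It is meant to assess whether results altered practice, and the content named is "change in disease monitoring, change in recommended treatment, referral to genetic counseling and other parameters". Under section 3.1 the form goes to the clinician of each patient who pursues testing, once results are back. The same section says that if a pathogenic mutation is found, "the patient will be referred to see the UCSD cancer medical genetics clinic for consultation with a genetics counselor".

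Appendix D is the form itself. Its item on current management reads "Did the results of germline testing change your management of this patient currently", and item 3 puts the same question for the future. Item 5 reads "Did the results of this testing lead to further diagnostic testing or referrals". Item 1 asks about helpfulness, item 4 about perceived prognosis, and item 6 invites further comments.

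Management information also comes from elsewhere. Section 3.5 takes management and surveillance data from the medical record over 24 months, and section 4.3 captures systemic therapy. Section 4.5.2 plans descriptive statistics for medical management, and section 4.5.3 a qualitative description of the impact on management and surveillance.

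**The concern.** The protocol's description of the form and the form itself do not match. Someone reading section 5.1.2 would expect the study report to say in how many tested men the result altered monitoring, in how many it altered recommended treatment, and in how many it led to a genetic counselling referral. Appendix D cannot supply those three counts. A Yes to item 2 could mean a new drug, a different surveillance schedule or something else.

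What is at stake is the informative part of a secondary endpoint. The report could give the proportion of tested men whose clinician says management changed or will change, but not a breakdown by type of change attributed to the result. Few carriers are expected, and a clinician's reasoning is hard to recover if it was not asked for at the time.

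**Working it through.** No power or sample-size formula applies. The check counts the items and maps them to the stated content.

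**Step 1: item count.** Appendix D has 5 closed items and 1 free-text item: 5 + 1 = 6. This reproduces the six stated in section 5.1.2, so the form appears complete and no item looks lost from the document.

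**Step 2: items against the domains named in section 5.1.2.**

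| Item | Subject | Answer | Monitoring | Recommended treatment | Genetic counselling referral |
|---|---|---|---|---|---|
| 1 | Helpfulness | Yes/No/Unsure | – | – | – |
| 2 | Management changed now | Yes/No/Unsure | not distinguished | not distinguished | – |
| 3 | Management will change | Yes/No/Unsure | not distinguished | not distinguished | – |
| 4 | Perceived prognosis | Yes/No/Unsure | – | – | – |
| 5 | Diagnostic testing or any referral | Yes/No/Unsure | – | – | merged |
| 6 | Further comments | optional text | unprompted | unprompted | unprompted |

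Domains with their own item: 0 of 3. Items asking directly whether management changed: 2 of 6 (items 2 and 3), with item 5 contributing in part.

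**Step 3: items against endpoint 3.** Items 2, 3 and 5 ask the clinician to attribute a change to the result, so whether management changed can be reported. The type of change appears only if a clinician volunteers it under item 6, which does not prompt for it.

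**Step 4: item 5 among carriers.** Section 3.1 requires a genetics referral after every pathogenic result. If that is followed, a truthful answer to item 5 is Yes for every carrier, whether or not anything else was ordered. The item then carries no information on further testing or other referrals in that group.

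**Step 5: how many men Step 4 affects.** Inputs:
- Men tested: 50 is the target accrual and so the upper end. The lower end of 25 (half of those enrolled) is an assumption.
- Carrier prevalence: Table 1 gives 6% for NCCN high-risk localized disease and 11.8% for metastatic disease. It is an assumption that the enrolled mix falls between these.

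Expected carriers = men tested × prevalence:
- Low end: 25 × 0.06 = 1.5
- High end: 50 × 0.118 = 5.9

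The non-carrier share of completed forms is 1 − 0.118 = 88.2% to 1 − 0.06 = 94%. Section 3.1 requires no referral for these men, so item 5 can vary among them.

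**The case against.** The strongest reply is that the form does its stated job. Section 5.1.2 gives its purpose as assessing whether practice altered. Items 2, 3 and 5 ask that and link it to the result, and monitoring and treatment both fall under management. This stands. A reader might infer from the mismatch that endpoint 3 cannot be answered from the form at all. The documents do not support that, because whether management changed can be described and item 6 may add detail.

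A second reply is that the chart fills the gap. Sections 3.5, 4.3 and 4.5.3 provide for management, surveillance and systemic-therapy data and a qualitative account of impact. This stands for the targeted-therapy hypothesis: prescribing is an observable fact that can be read from therapy data alongside the germline result. It would be wrong to infer that the hypothesis has no data source because the form has no treatment item. The reply does not rescue endpoint 3 as worded, since that is defined by physician responses, and a chart may show what was done without recording whether the test result was the reason.

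A third reply is that item 5 remains useful. Most forms will concern non-carriers, and a Yes for a carrier is a true answer. This stands too, so the item 5 problem is confined to separability among carriers.

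Finally, the endpoint is secondary and descriptive in a 50-patient pilot, and a handful of carriers can be described case by case. That limits the consequences. However, a case description of why management changed still needs the clinician's reason to have been collected.

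**Conclusion.** The point holds as a mismatch between section 5.1.2 and Appendix D, with a limited but real effect on secondary endpoint 3. None of the three named domains has its own item. The endpoint can be reported as Yes, No or Unsure with optional comments, and not by type of change. For carriers, about 1.5 to 5.9 men under the stated assumptions, item 5 cannot separate the required genetics referral from anything further.

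The count of 0 of 3 rests only on reading the form and needs no assumption. The number of carriers depends on the assumed number tested and on Table 1 applying to this clinic population. The primary endpoints are unaffected.

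**What to change.** In Appendix D:
- Under items 2 and 3, add tick-boxes for the type of change: disease monitoring, recommended treatment, other.
- Split item 5 into genetic counselling referral, other referral, and further diagnostic testing.
- State in section 4.5.2 that endpoint 3 will be reported by these categories.

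The cost is a short edit to one form and its database fields. The form may already be in use: the milestones plan final instruments for July 2021 and accrual from October 2021, and this protocol version is dated 12/06/2021. If so, there will be two form versions, which should be flagged in the data and reported separately for the items that changed.

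For forms already completed, say plainly that endpoint 3 gives whether management changed, and name chart review under section 3.5 as the source for the type of change and for targeted-therapy prescribing. Chart review has its own limit. With accrual from October 2021 and database lock planned for October 2022, no patient would have more than about 12 of the 24 months of follow-up at lock. The report should therefore state the follow-up available.
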